8.4 Adverse Event Reporting Procedures

The occurrence of AEs should be sought by nonleading questioning of the subject at each scheduled or unscheduled study visit. At each visit, study personnel should ask the following question: “Have you had any problems since your last visit?” An AE may also be detected when volunteered by the subject during and between visits, or through physical examination or other assessments. All AEs (serious and nonserious) reported by the subject will be reviewed by a qualified physician participating in the study and must be recorded on the subject’s source documents and AE CRF.

All SAEs, whether or not related to study drug, must be reported to the Sponsor or Sponsor’s designated Pharmacovigilance contact immediately and must be submitted on an SAE report form within 24 hours after the investigator becomes aware of the event.

If an SAE occurs, the study center should immediately notify Graybug Vision email notification: [contact]. The project manager will notify the medical monitor and/or the Sponsor immediately (within 24 hours).

Alternatively, the investigator may contact the medical monitor directly:

Note that any SAEs that occur after the subject has provided written informed consent, but before administration of study drug and are considered related to a protocol procedure must also be reported to the Sponsor or Sponsor’s designated project manager within 24 hours after the investigator’s awareness of the event.

Investigators should not wait to receive additional information to fully document an SAE before reporting the event to the Sponsor or Sponsor’s designated project manager. If only limited information is initially available, follow-up reports are required. Additional relevant information

such as hospital records, laboratory test results, or autopsy reports should be provided as soon as these are available.

8.5 Reporting Serious Adverse Events to Regulatory Agencies

An AE, whether serious or nonserious, is considered “unexpected” if the event is not reported in the clinical safety section of the reference document (eg, an IB or package insert) or if the event is of greater severity or frequency than is reported in the reference document.

Expedited reporting of SAEs is required for serious events that are both unexpected based on the reference document and considered related to the study drug (ie, the relationship cannot be ruled out). The Sponsor will determine which SAEs qualify for expedited reporting.

Reports of those SAEs that qualify for expedited reporting submitted to regulatory agencies in accordance with applicable local regulation (eg, 21 CFR 312.32).

Expedited reports will also be distributed to investigators. Upon receiving such notices, the investigator must immediately submit a copy of this information to the governing institutional review board (IRB) in accordance with the board’s guidelines and any applicable local regulations.

8.6 Pregnancy

Pregnancy alone is not an AE. However, any report of pregnancy in a female subject at any time during the study and that becomes known to the investigator, must be reported to the Sponsor even if the subject is withdrawn from the study. The pregnancy should be followed to term, reporting the outcome after delivery.

8.7 Overdose

Overdose is defined as any dose higher than the protocol-prescribed dose of study drug. Occurrences of overdose leading to an AE will be reported on the AE CRF. Overdoses leading to an SAE will be handled in accordance with SAE reporting procedures.

8.8 Follow-up of Adverse Events

Subjects with an ongoing SAE will be followed until the event is resolved, the significant changes return to baseline, the condition stabilizes, the event is no longer considered clinically significant by the investigator, the subject withdraws consent, or the subject is lost to follow-up. This may imply that follow-up will continue after the subject has left the study and that additional investigation may be requested by the Sponsor. If the severity or relationship to study drug worsens for an ongoing SAE, a follow-up report should be sent to the Sponsor within 24 hours after the investigator becomes aware of the change in status.

All nonserious AEs will be followed through the last study visit. If a nonserious AE is first identified at the last scheduled study visit, the event will be recorded on the AE CRF with the current status noted, but no further follow-up is required.

9 STATISTICAL CONSIDERATIONS

9.1 General Methods of Analysis

No formal hypothesis testing will be conducted

General descriptive statistics will be used to evaluate the data (eg, means, median, ranges, standard deviations). All summaries will be presented by treatment group and, where appropriate, by visit.

9.2 Study Endpoints

9.2.1 Primary Endpoint

- Occurrence of ocular and nonocular AEs and SAEs

9.2.2 Secondary Pharmacodynamic Endpoints

- BCVA at all study visits
- CST at all study visits
- Observed subjects who are rescue-free at each study visit

9.3 Analysis Populations

Three analysis sets will be defined as follows:

- **Safety analysis set (SS):** Includes all subjects who receive a dose of study treatment. Subjects who receive rescue treatment during the study will be included in the SS. Analyses will group subjects according to the treatment actually received.
- **Full analysis set (FAS):** Includes all subjects who receive a dose of study treatment, and complete the baseline and at least one post-baseline visit. All data collected from subjects who receive rescue treatment during the study will be included in the FAS. Subjects will be analyzed according to their assigned treatment regardless of actual treatment received. The analyses conducted on the FAS will be considered primary for all efficacy analyses.
- **Per protocol analysis set (PP):** Consists of a subset of the FAS and includes subjects with no major protocol violations that would affect the assessment of the pharmacodynamics and rescue data. Data collected after the receipt of rescue therapy during the study will not be included in PP analyses. The PP analyses will be considered secondary for all efficacy analyses.

9.4 Sample Size Considerations

The sample size of this study was not selected to support specific statistical hypothesis testing. A sample size of approximately 20 evaluable subjects in the SS analysis set allows for detection of adverse events rates that exceed 15% overall and exceed 30% for each dose with approximately 95% confidence.

9.5 Analyses

9.5.1 Safety Analyses

All reported adverse events will be coded using the Medical Dictionary for Regulatory Activities (MedDRA). Treatment-emergent adverse events (TEAEs) will be summarized by system organ class (SOC) and preferred term (PT). Frequencies and percentages will be provided by treatment group for subjects with TEAEs, treatment related TEAEs, serious TEAEs, serious treatment related TEAEs, TEAEs leading to premature study discontinuation, and TEAEs by maximum severity. Separate analyses will be performed for ocular AEs in the study eye, ocular AEs in the non-study eye, and nonocular AEs.

The SS will be the primary population used for analysis of the primary safety endpoint.

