Number of Subjects Planned: Approximately 20 subjects are planned: 10 subjects treated with 1 mg GB-102 and 10 subjects treated with 2 mg GB-102. There is no pre-set limitation on the proportion of DME or RVO subjects per dose group.

Target Population: Subjects eligible for screening must have a history of macular edema in the **study eye** secondary to DME or RVO that was diagnosed in the 6 weeks to 24 months prior to screening, treated with at least 3 prior intravitreal (IVT) injections of anti-VEGF (aflibercept, bevacizumab, or ranibizumab), and demonstrated a response anti-VEGF treatment. The most recent anti-VEGF treatment must be administered within 42 days of screening.

The investigator will interpret SD-OCT used to determine subject eligibility; there is no third-party independent reading center confirmation of any images during screening or treatment/observation.

Duration of Study Participation: Approximately 210 days (up to 30 days for screening and 180 days of treatment/observation)

Inclusion Criteria: **All Subjects (DME or RVO)**

1. Verbal and written informed consent obtained from the subject
2. Males or females ≥ 21 years of age
3. Willing and able to give informed consent, comply with all study procedures, and be likely to complete the study
4. Subjects with known diagnosis of diabetic macular edema or macular edema due to retinal vein occlusion (central or branch) in the 6 weeks to 24 months prior to screening who have received at least 3 prior IVT injections of any anti-VEGF agent in the **study eye** and demonstrated a pharmacodynamic response in the **study eye** to IVT anti-VEGF treatment (aflibercept, bevacizumab, or ranibizumab) within 16 weeks of the first anti-VEGF treatment as

determined by the investigator and documented by **at least 1** of the following:

- 4a. Reduction of intraretinal/subretinal fluid by $\geq 10\%$ from the initial diagnosis as determined using SD-OCT
- 4b. Reduction of excess CST by $\geq 10\%$ from the initial diagnosis as determined using SD-OCT (assuming nominal thickness is 300 microns)
5. Demonstrate a maintained anti-VEGF response (as determined by the investigator) compared with the initial diagnosis (prior to any anti-VEGF treatment) as assessed by SD-OCT following the most recent anti-VEGF injection (defined as reduction in central subfield thickness, intraretinal/subretinal fluid, or maintenance of a dry retina)

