1.5.1.3 Toxicology

Sunitinib malate was originally developed as an orally administered agent for the treatment of advanced malignancies at a daily dose of 37 to 50 mg (SUTENT® capsules). The steady state plasma levels of sunitinib at the oral recommended daily dose is approximately 60 to 100 ng/mL. Based on allometric scaling from nonclinical ocular PK studies (rabbits, rats) to humans, it is estimated that a single orally administered approved dose of 50 mg sunitinib in man results in uveal tissue concentration of drug that are 1-log to 2-log orders higher than a single IVT injection of GB-102 containing 1 mg sunitinib (Peterson 2016, Speed 2012).

Three GLP ocular toxicology studies were conducted with GB-102: a single dose study in rabbits, a repeat dose study in rabbits, and a repeat dose study in minipigs.

The ocular toxicity following a single IVT injection (50 µL) of GB-102 at doses of 0, 0.25, 0.5, 1.0, and 2.0 mg/eye in pigmented rabbits was evaluated in a GLP study with up to 19 weeks observation. Assessments were conducted with *in vivo* ophthalmic examination, including ERGs, and postmortem histopathology of the enucleated eyes. The main findings included 1) time- and dose-dependent lens opacities, which were due to the high injection volume (50 µL), and 2) mild anterior and vitreous inflammation, which was due to endotoxin contamination of the test materials.

In the repeat-dose rabbit study, animals received IVT injections of 0.125, 0.25 and 0.5 mg/eye GB-102 (in volumes up to 12 µL). Animals were injected on Day 1 and Day 141 over the course of 40 weeks. GB-102 was well tolerated compared to the GLP single dose ocular toxicology study in rabbits. The main findings in the repeat dose rabbit study included transient ocular inflammation at all dose levels regardless of dose volume, which was not test article related. Focal, peripheral and inferior lens opacities occurred in 3 out of 4 groups, which were test article related.

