- An important medical event or serious medical condition that does not meet any of the above criteria may be considered an SAE if, based upon appropriate medical judgment, it jeopardizes the subject or requires medical or surgical intervention to prevent one of the outcomes listed above. Examples of such medical events include allergic bronchospasm requiring intensive treatment in an emergency room or at home, blood dyscrasias, or convulsions that do not result in in-patient hospitalization, or the development of drug dependency or drug abuse.

An overall summary will be presented that includes the number of TEAEs and the number and percentage of subjects who experienced at least one TEAE, total and by cohort. This summary will also include breakdowns of TEAEs further categorized as ocular (study eye and non-study eye, separately), non-ocular, serious TEAEs, TEAEs by maximum severity, treatment-related TEAEs, and TEAEs leading to subject withdrawal.

Additional summaries of TEAEs will be provided showing the number and percentage of subjects who experienced at least one TEAE and total number of events. These summaries will be presented by SOC and PT. Non-ocular TEAEs will be summarized using discrete summary statistics and presented by cohort and total subjects at the subject and event level by SOC and PT. Ocular TEAEs will be similarly summarized at the subject level for study and non-study eyes separately. If a subject has multiple TEAEs coded to the same PT within same SOC, that PT will only be reported once. As with the PT, if a subject reports multiple conditions within the same SOC, that SOC will only be reported once at the subject level. In the summary, SOCs are listed in order of decreasing frequency for total subjects. PTs are listed in order of decreasing frequency within each SOC for total subjects. The occurrence of non-ocular and ocular TEAEs will also be tabulated by SOC and PT for the following: maximal severity and suspected relationship to study drug.

Separate summaries will be provided for the following categories of AEs:

- Ocular TEAEs in the study eye
- Ocular TEAEs in the non-study eye
- Non-ocular TEAEs
- Treatment-related ocular TEAEs in the study eye
- Treatment-related ocular TEAEs in the non-study eye
- Treatment-related non-ocular TEAEs
- Ocular serious TEAEs in the study eye
- Ocular Serious TEAEs in the non-study eye
- Non-ocular serious TEAEs
- Treatment-related ocular serious TEAEs in the study eye

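### No planned table gives, by dose, the number of subjects who ever have intraocular inflammation or a lens opacity event in the study eye

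*Protocol*

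**What the plan says.** The primary endpoint is the occurrence of ocular and nonocular adverse events. For its analysis, Protocol 9.5.1 says: "Treatment-emergent adverse events (TEAEs) will be summarized by system organ class (SOC) and preferred term (PT"). SAP 13.1 gives the counting rule: "If a subject has multiple TEAEs coded to the same PT within same SOC, that PT will only be reported once". A subject is likewise counted once per SOC. The tables in SAP 15 cross these two levels with eye, relatedness, seriousness, maximum severity and site. The overall summary adds any ocular event per eye. Neither document defines a grouped term or an event of special interest.

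Examination findings are reported separately. SAP 13.3 tabulates AREDS nuclear, cortical and posterior subcapsular scores and anterior chamber cells and flare, with shifts from baseline at each follow-up visit (Tables 14.3.9.1 and 14.3.9.3). SAP 13.4 reports the vitreous as normal, abnormal not clinically significant, or abnormal clinically significant. Protocol Appendix 18.4.3 has a vitreous haze grade, but no SAP table uses it.

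Protocol 1.5.1.3 names two main findings in the single-dose rabbit study: "time- and dose-dependent lens opacities, which were due to the high injection volume", and "mild anterior and vitreous inflammation", which it puts down to endotoxin contamination. In the repeat-dose rabbit study it calls the lens opacities test-article related and the inflammation not.

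**The concern.** Intraocular inflammation may be recorded as, for example, iritis, uveitis, vitritis or anterior chamber cells, and a lens change under one of several opacity or cataract terms. A preferred-term row counts one of these. The SOC row pools them with every other event in the class. The clinical question, how many of the 10 eyes at each dose ever became inflamed or developed a lens opacity, lies between the two levels.

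The trial is open label and has a safety interim. If the groups are not fixed in advance, anyone who wants these rates must choose the terms after seeing the events.

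**Working it through.** **Inputs.** Group size: "10 subjects treated with 1 mg GB-102 and 10 subjects treated with 2 mg GB-102". Detection statement (Protocol 9.4): the study "allows for detection of adverse events rates that exceed 15% overall and exceed 30% for each dose with approximately 95% confidence". No test is planned: "No formal hypothesis testing will be conducted". The documents give no number of terms and no event data, so the split is an assumption throughout.

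**1. The plan's own figure.** The rule of three gives 3/20 = 15% and 3/10 = 30%. Exactly, the chance of at least one event is 1 − 0.85^20 = 96.1% for 20 subjects and 1 − 0.70^10 = 97.2% for 10. The statement reproduces. It concerns seeing at least one event in one category.

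**2. What each output counts.**

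| Output | Unit counted | Any-time subject count for the concept? |
|---|---|---|
| Preferred-term row | subjects with that term | No, one term only |
| SOC row | subjects with any event in the class | No, mixed with other events |
| Table 14.3.9.3 (cells, flare, AREDS) | subjects by grade, at one visit, for one parameter | No, not across visits or parameters |
| Table 14.3.10.2 (vitreous) | subjects by three-level status, at one visit | No, and not combined with anterior findings |

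**3. The rows cannot simply be added.** A subject with two related terms counts once in each row. Suppose three related rows each show 1/10. The number of subjects affected is then anything from 1 (the largest row) to 3 (the sum), that is 10% to 30%. The exact 95% interval is 0.3% to 44.5% for 1/10 and 6.7% to 65.2% for 3/10. The visit tables behave similarly: three transient cases at three different visits show as 1/10 each time.

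**4. Illustration of splitting.** Assume a true 30% rate in one group of 10, three terms and one term per subject.

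- P(3 or more affected) = 1 − 0.028 − 0.121 − 0.233 = 0.617 (binomial, 0, 1 and 2 events removed).
- P(3 or more affected and no term at 3 or more), by exact multinomial enumeration: 0.413 for 10/10/10%, 0.276 for 20/5/5%, 0.169 for 24/3/3%.
- Dividing by 0.617 gives **67%, 45% and 27%**.
- For one given term at 10%, P(at least 1) = 1 − 0.9^10 = 65.1% and P(at least 2) = 26.4%. A grouped row gives 97.2% and 85.1%.
- With an even split over two or five terms, P(at least 1) for one given term is 80.3% or 46.1%.
- P(at least one event in some row) = 1 − 0.70^10 = 97.2%, whatever the split.

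**The case against.** The case against is strong in several respects.

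- A reader might infer that these findings are shown only through coded terms, or that their rate cannot be found at all. The documents do not support that. AREDS scores, cells and flare are tabulated by cohort and eye with baseline shifts, independently of coding, and Listings 16.2.7.1, 16.2.8.2 and 16.2.8.3 would allow a rate to be rebuilt. But rebuilding requires a grouping, and none is specified.
- A reader might infer that terms will scatter widely. Protocol 8 prefers a diagnosis, and Protocol 8.1 asks investigators to gather the signs of one diagnosis under one term. That reduces splitting within a subject. It does not make different investigators use the same diagnosis.
- A reader might infer that splitting defeats the 30% detection statement. It does not: on the at-least-one-event reading the chance stays 97.2%. The 3/10 cut-off behind the 67%, 45% and 27% is an illustration that the documents do not use.
- A reader might take the toxicology as evidence that the drug causes inflammation. Protocol 1.5.1.3 attributes the single-dose inflammation to endotoxin and the opacities to injection volume, and reports the minipig study as well tolerated. What stands is that the repeat-dose rabbit opacities are called test-article related, and that the sponsor chose to grade inflammation and lens opacity in this trial.
- With about 20 open-label subjects and ongoing review by the medical monitor, a cluster of cases is unlikely to go unseen. I agree. The gap lies in what the primary safety tables report, not in surveillance.

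**Conclusion.** The point holds as a reporting gap, and fixing it is a cheap improvement. No planned table states the any-time, per-subject incidence by dose of intraocular inflammation or of a lens opacity event in the study eye. This follows from the table list alone and needs no assumption.

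The size of the effect does rest on assumptions: a 30% true rate, three terms and one term per subject. On those, a count of 3 or more in 10 would not appear as 3/10 under any one term in 27% to 67% of cases, depending on how unevenly the terms divide. If all investigators use one term, nothing is lost in the adverse event tables. The SOC and preferred-term plan is otherwise complete, and the documents do not support saying that a safety signal would be missed.

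**What to change.** Before the Month 3 safety interim:

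1. In SAP 13.1, list the preferred terms for two groups: intraocular inflammation (anterior and vitreous) and lens opacity or cataract.
2. Add one subject-level study-eye row for each group, by cohort and total, to Tables 14.3.1.1 and 14.3.2.1. Both are already in the topline delivery.
3. Add a worst post-baseline shift for cells, flare and AREDS scores to Table 14.3.9.3. First reconcile the AREDS scale: Protocol Appendix 18.5 grades +1 to +3, while SAP 13.3 uses scores from <1 to >3.
4. Tabulate vitreous haze, if the grade is recorded.

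I would not add further groups on this argument. SAP 13.5 already defines and summarises clinically relevant IOP change, and nothing above supports a grouping for depot displacement.

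The cost is a term list and a few table rows, with no new data.

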#### 5. Sample Size

The sample size is within clinical standards for the establishment of preliminary safety of GB-102. The sample size of this study was not selected to support specific statistical hypothesis testing. A sample size of approximately 20 evaluable subjects in the FAS analysis set allows for detection of adverse events with rates that exceed 15% overall and exceed 30% for each dose with approximately 95% confidence.

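### Adverse event incidence, the primary endpoint, is reported as counts and percentages only, with no confidence limit to show which rates the data exclude

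*Protocol*

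**What the plan says.** Protocol 9.2.1 and SAP 3 make the occurrence of AEs and serious AEs the primary endpoint.

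On size, Protocol 9.4 states that "The sample size of this study was not selected to support specific statistical hypothesis testing". It then gives one quantitative statement: "A sample size of approximately 20 evaluable subjects in the SS analysis set" permits "detection of adverse events rates that exceed 15% overall and exceed 30% for each dose with approximately 95% confidence". The synopsis and Protocol 3.2 repeat this. SAP 5 gives the same figures, "detection of adverse events with rates that exceed 15% overall and exceed 30% for each dose with approximately 95% confidence", but attaches them to the full analysis set. SAP 5 also describes the size as in line with usual clinical practice for a first look at safety. The split is "10 subjects treated with 1 mg GB-102 and 10 subjects treated with 2 mg GB-102" (Protocol synopsis).

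On output, Protocol 9.5.1 says "Frequencies and percentages will be provided by treatment group for subjects with TEAEs" and then lists further categories such as treatment-related and serious events. SAP 13.1 plans an overall summary with event counts and "the number and percentage of subjects who experienced at least one TEAE, total and by cohort", followed by tables by system organ class and preferred term. SAP 8.4 limits summaries of discrete variables to a number and a percentage, the latter to one decimal place. SAP 1 says that its methods replace those in the protocol.

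No confidence interval or upper bound for an AE incidence appears in the protocol analysis section, the SAP text or the SAP table list. The term itself is found only in the protocol's abbreviation list.

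**The concern.** A trial of 10 subjects per dose can say little about uncommon events. What it can usefully say is how high a rate remains compatible with the data. The plan uses that idea to explain what about 20 subjects can do, and then does not carry it into the results.

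The consequence is clearest for zero counts. Under the SAP 8.4 rounding rule, a category with no events in a dose group prints as 0.0%. A reader who sees only that figure may take the event to be absent, when a true rate of a quarter or more has not been excluded. The tables most exposed are those read first: 14.3.1.1 (overall AE summary), 14.3.2.1 (ocular events, study eye), 14.3.4.1 (ocular serious events, study eye) and 14.3.4.3 (non-ocular serious events). All four are marked for topline delivery.

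**Working it through.** **Inputs.** About 20 subjects in all, 10 per dose (synopsis, Protocol 9.4). Stated detectable rates 15% and 30% at about 95% confidence (Protocol 9.4, SAP 5). The documents do not say whether this is one-sided or two-sided.

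**Step 1: reproduce the plan's figures.** The rule of three puts the approximate 95% upper bound for zero events in n subjects at 3/n.

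- Overall: 3/20 = 15.0%.
- Per dose: 3/10 = 30.0%.

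Both match exactly. As an exact check, the probability of seeing at least one event at true rate p is 1 − (1 − p)^n.

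- n = 20, p = 0.15: 1 − 0.85^20 = 96.1%.
- n = 10, p = 0.30: 1 − 0.70^10 = 97.2%.

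The statement is sound and slightly conservative. A probability of 95% needs ln 0.05 / ln 0.85 = 18.4 subjects overall and ln 0.05 / ln 0.70 = 8.4 per dose.

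**Step 2: limits when no event is seen.** The one-sided exact 95% upper limit is 1 − 0.05^(1/n). This is also the true rate at which the chance of at least one event is exactly 95%, so it is the limit that corresponds to the detection statement. The two-sided exact limit is 1 − 0.025^(1/n).

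| Result | Printed | One-sided 95% upper | Two-sided 95% upper |
|---|---|---|---|
| 0/10 | 0.0% | 25.9% | 30.8% |
| 0/20 | 0.0% | 13.9% | 16.8% |

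**Step 3: two-sided exact intervals for small counts.** For x events in n, the Clopper-Pearson limits are the 0.025 quantile of Beta(x, n − x + 1) and the 0.975 quantile of Beta(x + 1, n − x).

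| Result | Percentage | Exact 95% interval |
|---|---|---|
| 1/10 | 10.0% | 0.3% to 44.5% |
| 2/10 | 20.0% | 2.5% to 55.6% |
| 1/20 | 5.0% | 0.1% to 24.9% |
| 2/20 | 10.0% | 1.2% to 31.7% |

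**Step 4: sensitivity to the final numbers.** The planned size is approximate, and Protocol 6.6 lets a treated subject who withdraws before Month 3 be replaced, so a group may not end at exactly 10. For zero events, the one-sided and two-sided upper limits are 31.2% and 36.9% with 8 subjects, 28.3% and 33.6% with 9, and 23.8% and 28.5% with 11. Limits should use the actual safety-set denominators.

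**The case against.** The strongest reply is that the sizing sentence concerns detection: the chance, before the trial, of seeing an event at least once. Counting events is how detection is delivered, and the tables count them. The endpoint is occurrence, not a rate estimated to a stated precision. This stands to the extent that nothing in the plan is contradictory and no promised output is missing. It does not explain why the primary results should carry no precision at all, since at zero events the detection rate and the one-sided upper limit are the same number.

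A second reply is that the study is descriptive and exploratory, with no testing. That is true, but an exact interval is a descriptive summary and needs neither a hypothesis nor a multiplicity adjustment.

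A third is that two-sided zero-event limits (30.8%, 16.8%) lie above the stated 30% and 15%, so on their own they would appear to fall short of the plan's claim. This is correct, and is why the one-sided limit is needed for zero counts.

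A fourth is that tables by preferred term list events that occurred, so a term seen in neither dose has no row and no interval. This also stands. A footnote has to cover that case.

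Several stronger readings are tempting, and the documents do not support them:

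- That all safety tables are counts and percentages. Visual acuity, intraocular pressure and vital-sign changes have continuous or change-from-baseline summaries, and AE tables also give event counts. The point concerns AE incidence.
- That the sample size was derived from the 95% statement. Protocol 9.4 says only what about 20 subjects make possible, and SAP 5 also appeals to customary size.
- That overlapping intervals settle whether the doses differ. Overlap of separate intervals is not a valid comparison, and the plan makes none.
- That rescue proportions need the same treatment for the same reason. They are a pharmacodynamic output unconnected with the AE sizing statement.

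**Conclusion.** The point holds as a minor, inexpensive improvement to reporting. The only quantitative justification for about 20 subjects is a 95% confidence statement about AE rates, and every planned AE incidence table stops at counts and percentages. With no events, the data still allow rates up to 25.9% (one-sided) or 30.8% (two-sided) per dose, and 13.9% or 16.8% overall; the printed value is 0.0% in each case.

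These figures assume 10 subjects per dose in the safety set, independent subjects and a common event rate within each group. Reading the 15% and 30% as 3/n is an inference, because the plan gives no derivation, but both values match exactly. Neither the data collected nor the design is affected.

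**What to change.** In SAP 8.4, allow an exact interval for subject-level AE incidence. In SAP 13.1, specify:

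- Clopper-Pearson two-sided 95% confidence intervals, by dose and in total, for the category-level incidences: any, ocular study-eye, treatment-related and serious treatment-emergent events. Show them in Tables 14.3.1.1, 14.3.2.1, 14.3.4.1 and 14.3.4.3, and print these rows even when the count is zero.
- For zero counts, also the one-sided 95% upper limit, labelled as the one that matches the detection statement (25.9% for 0/10, 13.9% for 0/20, recalculated for the actual denominators).
- A footnote giving that one-sided limit for any event not observed, since such events have no row.

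Keep the statement that no testing is done, add that dose groups are not to be compared by interval overlap, and leave the rescue table as it is.

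The cost is one extra column in four tables and a footnote. The intervals will be wide, which is a fair picture of what 10 subjects per dose can show.
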